# **Probiotics as Adjuvant Treatment for Bacterial Vaginosis**

**NCT03894813**

**2021-02-20**

## Study Protocol with SAP

This study was a single-centre, prospective, parallel-group, randomized, controlled study. Women who came to the gynaecological clinic of Peking University Shenzhen Hospital, China, between March 2019 and June 2019 with abnormal vaginal discharge symptoms were recruited, and eligible subjects were informed of the study protocol and enrolled in the study. The inclusion criteria were women aged between 18 and 65 years old, premenopausal women, women with a history of sexual activity, and women with a Nugent's Gram stain score of 7 or higher. The exclusion criteria were mixed vaginitis, such as vulvovaginal candidiasis (VVC), Trichomonas vaginalis (TV) infection, *Chlamydia trachomatis* (CT) infection or gonococcal vaginitis; planning for or being pregnant; breast-feeding; pelvic inflammatory disease; allergy to metronidazole; currently using antibiotics; long-term use of contraceptives or immunosuppressants or anaphylactic constitution; and a history of systemic organic diseases or psychiatric diseases. The study was conducted in accordance with the Declaration of Helsinki, was approved by the Medical Ethnic Committee of PKUSZH (with the Unique Protocol ID: PUShenzhenH2018-016) and was first posted on ClinicalTrials.gov (NCT03894813) on March 26, 2019. Informed consent was obtained from all subjects involved in the study.

The sample size was calculated based on the non-inferiority test (<https://www.cnstat.org/samplesize/12/>), which referred to Gregor Reid et al, who carried out studies with the same Lactobacillus strains administered orally to women with bacterial vaginosis (BV). The relevant parameters were determined as follows: test level  $\alpha=0.05$ , test power  $1-\beta=0.80$ ,  $Pt=0.90$ ,  $Pc=0.75$ ,  $Nt:Nc=1:1$ , boundary value  $\Delta= -0.068$  (excellent), and Fisher's exact test. As a result, the sample size of each group was calculated as 50 patients, 100 patients in total. Considering a loss to follow-up rate of 20%, a sample size of 120 patients was finally determined, with 60 patients in each group.

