After obtaining written informed consent, the participants were first asked to complete a questionnaire on demographic characteristics, reproductive health and sexual behaviour. They were subsequently randomly assigned to either the metronidazole group or the adjunctive probiotic group according to the random number table. The study was not blinded to the researchers or the patients. Starting from the enrolment day, the participants in the adjunctive probiotic group received orally administered probiotic drinks containing *L. rhamnosus* GR-1 and *L. reuteri* RC-14 ( $\geq 1 \times 10^9$  CFU per day, for 30 days) and vaginally administered metronidazole suppositories (0.2 g per day, for 7 days), and the participants in the metronidazole group received metronidazole vaginal suppositories only. Clinical follow-up visits were scheduled at 30 and 90 days after starting treatment. The intervention products were dispensed by the investigator at the initial visit, and the compliance of participants was assessed by counting returned containers and filling out a questionnaire. The feasibility, acceptability and adherence to the administered products; vaginal symptoms; and

adverse events (AEs) were also assessed by self-report in medication diaries and questionnaires at follow-up visits. Therapy was initiated after the enrolment visit and suspended when menstruation began and continued immediately when it finished. Patients were asked to avoid sexual intercourse and vaginal douching during the first 7 days of treatment with metronidazole suppositories.

General information and clinical signs and symptoms of BV, including homogeneous and thin vaginal discharge, unpleasant odour (such as a “fishy” smell) and vulvar discomfort (such as itching or burning), were recorded at 0 day, 30 days and 90 days. The efficacy outcome was evaluated by the cure rate according to per-protocol (PP) analysis, which was the percentage of participants who did not present with BV (defined by Nugent score  $< 7$ ) at any of the follow-up visits. Those with a Nugent score  $\geq 7$  in the 30-day follow-up was excluded from the trial, but when we evaluate the overall recurrence rate of the 90-day follow-up, these participants were still included in. At each follow-up visit, patients were requested to report any unexpected symptoms during the study period. AEs were recorded in the case report form (Table S1).

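### The cure rate is analysed only in an undefined per-protocol set, with no all-randomised analysis beside it, in an open-label trial sized for non-inferiority

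*Combined protocol and SAP*

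**What the plan says.** The document has one heading, Study Protocol with SAP, so places are given by paragraph.

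- **Outcome paragraph.** "The efficacy outcome was evaluated by the cure rate according to per-protocol (PP) analysis". The clause that follows defines cure (Nugent score below 7 at follow-up), not membership of the PP set. Women scoring 7 or more "in the 30-day follow-up was excluded from the trial", and are put back for the overall 90-day recurrence rate.
- **Randomisation and treatment paragraph.** "The study was not blinded to the researchers or the patients". The probiotic arm had a 30-day drink and 7 days of suppositories, whereas "the participants in the metronidazole group received metronidazole vaginal suppositories only". Adherence was measured: "the compliance of participants was assessed by counting returned containers and filling out a questionnaire". No threshold is attached to that measurement.
- **Sample size paragraph.** "The sample size was calculated based on the non-inferiority test", with rates of 0.90 and 0.75, a margin of -0.068, 50 per group, and 60 per group after a 20% allowance for loss to follow-up.
- **Diagnosis paragraph.** Two technicians read the slides blind.

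Nowhere is there an intention-to-treat, full-analysis or all-randomised set, a list of disqualifying deviations, or a rule for missing Nugent results. The text is continuous at these points, with no sign of redaction or a lost table.

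**The concern.** Randomisation protects the comparison only for the women as randomised. A PP set is chosen after randomisation, here by people who knew the treatment, under a rule the plan does not state and with more ways to be non-adherent in one arm. If women leave the set at different rates by arm, and cure at a different rate from those who stay, the comparison can create a difference or hide one.

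Non-inferiority makes this a two-sided problem. Including non-adherent women can shrink a true deficit and so favour non-inferiority, which is why PP deserves a place. Leaving them out can break the balance between arms. Each set can mislead in its own way, so a reader needs both. The planning rates also favour the probiotic arm by 15 points, so readers will look for added benefit, and an undefined PP set alone is weak support for that claim.

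**Working it through.** **Reproducing the plan's 50 per group.** From the sample size paragraph: rates 0.90 and 0.75, margin 0.068, power 0.80, 1:1. The distance from the margin is d = 0.90 - 0.75 + 0.068 = 0.218. The variance term is v1 = 0.90×0.10 + 0.75×0.25 = 0.2775. With the rates constrained to differ by exactly the margin (restricted maximum likelihood: 0.776 and 0.844), v0 = 0.3055. The Farrington-Manning formula at one-sided 0.025 gives

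n = (1.960√0.3055 + 0.842√0.2775)² / 0.218² = 49.05, rounded up to 50.

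The unpooled formula gives 46. The match with 50 is inferred: the plan cites an online calculator and Fisher's exact test, and does not say whether α = 0.05 is one- or two-sided. Power is therefore shown below at one-sided 0.025 / 0.05.

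**(a) What PP alone can do.** All exclusion shares here are hypothetical; the plan's 20% is loss to follow-up, not PP exclusion. Let true cure be 0.75 in both arms, e the share outside PP, and c their cure rate. Then

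PP cure rate = (0.75 - e·c) / (1 - e).

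| c | e = 20% | e = 10% | e = 5% | False difference, 20% v 5% | False difference, 10% v 5% |
|---|---|---|---|---|---|
| 25% | 87.50% | 80.56% | 77.63% | +9.9 | +2.9 |
| 50% | 81.25% | 77.78% | 76.32% | +4.9 | +1.5 |
| 65% | 77.50% | 76.11% | 75.53% | +2.0 | +0.6 |
| 75% | 75.00% | 75.00% | 75.00% | 0 | 0 |
| 90% | 71.25% | 73.33% | 74.21% | -3.0 | -0.9 |

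Differences are probiotic minus control, in percentage points, with the larger exclusion in the probiotic arm. Signs reverse if it is in the control arm. Equal exclusion with equal c gives 0.

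**(b) How much an all-randomised analysis recovers.** Let a share s of the excluded women have given a slide. The lost fraction is e(1 - s). If imputation learns nothing beyond arm, it returns (0.75 - e(1 - s)c) / (1 - e(1 - s)). In the 20% v 5% case the error left is:

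| c | s = 0 | s = 0.5 | s = 1 |
|---|---|---|---|
| 25% | +9.9 | +4.3 | 0 |
| 50% | +4.9 | +2.1 | 0 |
| 90% | -3.0 | -1.3 | 0 |

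**(c) Why PP should stay.** Suppose the true deficit is 8.5 points among women who take the drink, and 20% of the probiotic arm do not take it and cure like controls. The all-randomised deficit is 8.5 × (1 - 0.20) = 6.8 points, exactly the margin.

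**(d) Power cost of requiring both sets.** 60 × 0.80 = 48 women per arm with slides; assume 5 per arm fall outside PP, leaving 43. Results are from 1,000,000 simulated trials at 0.90 v 0.75, using the restricted-variance test on women with slides:

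| Non-adherent probiotic women cure at | All-randomised | PP | Both |
|---|---|---|---|
| 0.90 | 0.81 / 0.89 | 0.78 / 0.86 | 0.75 / 0.85 |
| 0.75 | 0.73 / 0.84 | 0.78 / 0.86 | 0.70 / 0.81 |

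For comparison, the formula that gives the plan's 50 yields 0.79 / 0.87 at 48 per arm. Counting missing as not cured, with 20% loss in both arms, changes the rates to 0.90×0.8 = 0.72 and 0.75×0.8 = 0.60. With 60 per arm the same formula then gives 0.58 / 0.70.

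**The case against.** PP analysis is an accepted part of non-inferiority trials, the endpoint is a laboratory score, and the slides were read blind. The larger figures in (a) also sit awkwardly with the mechanism offered for them. A woman left out for not taking the drink was still assigned the same metronidazole; if she cures like a control, the table gives no bias. The +9.9 needs excluded women to cure at 25% against 87.5% among those kept, a gap with no basis in the documents. At 65% the figure is +2.0. The dilution example in (c) is likewise chosen to land on the margin. If PP in practice means completers, few excluded women have slides, and by (b) an all-randomised analysis removes little of the error. Finally, the both-sets rule and multiple imputation are choices among defensible options.

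Much of this stands as a limit on size. The scenarios are illustrations, zero and negative bias are among them, and the documents show no actual bias. The reliance on imputation for women lost to follow-up is real. It does not remove the defect. Blind reading protects the score, not the choice of who is analysed. Putting day-30 failures back for 90-day recurrence restores one group for one rate; it does not restore lost or non-adherent women to the cure analysis. Defining PP and adding the all-randomised analysis do not depend on the both-sets rule or on the imputation method.

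**Conclusion.** The concern holds. The only efficacy analysis uses a population that a reader cannot reconstruct from the plan, and no analysis as randomised stands beside it. That is certain from the text. The size and direction of any bias are unknown, because the documents give no PP exclusions by arm. With true cure of 75% in both arms, the 20% v 5% scenarios run from -3.0 to +9.9 points and the 10% v 5% scenarios from -0.9 to +2.9. The upper part of the first range exceeds the 6.8-point margin. There is no bias if exclusion is equal and excluded women cure equally in both arms, or if excluded women cure like those who stay. The fault is that PP is alone and undefined, not that it is used.

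**What to change.** Replace the single PP statement with text to this effect:

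*The cure rate is analysed in all randomised women in the arm assigned, regardless of adherence, and in a PP set defined by a stated adherence threshold and required visits. Both results are reported with equal prominence. Non-inferiority is concluded only if both sets support it; any claim of added benefit rests on the all-randomised analysis. Women with Nugent ≥ 7 at day 30 stay in the denominator as not cured. Missing Nugent results are handled by multiple imputation using arm, baseline Nugent, recorded symptoms and any day-30 Nugent, with missing = not cured and other departures as sensitivity analyses. Exclusions are reported by arm and reason.*

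The plan should also say whether cure is cumulative over both visits or assessed at each visit. Day-30 failures count as not cured on either reading.

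The document is dated 2021-02-20 and describes, in the past tense, women who "between March 2019 and June 2019 with abnormal vaginal discharge symptoms were recruited". If the data have already been seen, the PP rule must be labelled as set afterwards.

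**Cost.** No new patients and a little more analysis; the estimated effect may be smaller. Under the assumptions in (d), requiring both sets takes power from 0.78 / 0.86 for PP alone to 0.75 / 0.85, or to 0.70 / 0.81 if the non-adherent probiotic women cure at 0.75. For women lost to follow-up, the all-randomised result rests on the imputation assumptions, so these must be stated.

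### The trial is sized for non-inferiority at -0.068, but the plan states no between-group estimate, confidence interval or decision rule against that margin

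*Combined protocol and SAP*

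**What the plan says.** All references are to the combined protocol and SAP, section Study Protocol with SAP.

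- **Sample-size paragraph.** "The sample size was calculated based on the non-inferiority test". The inputs follow in a sentence that opens "The relevant parameters were determined as follows: test level": alpha 0.05 (one- or two-sided not stated), power 0.80, cure rates 0.90 (test) and 0.75 (control), 1:1 allocation and a boundary of -0.068. The list ends "excellent), and Fisher's exact test". The result is "As a result, the sample size of each group was calculated as 50 patients, 100 patients in total", and then "Considering a loss to follow-up rate of 20%, a sample size of 120 patients was finally determined", 60 per group.
- **Efficacy outcome paragraph.** "The efficacy outcome was evaluated by the cure rate according to per-protocol (PP) analysis". The text then defines that rate: "which was the percentage of participants who did not present with BV" (Nugent score below 7) at any of the follow-up visits. The next sentence says that women scoring 7 or more "in the 30-day follow-up was excluded from the trial", yet they stay in the overall 90-day recurrence rate.
- **Remaining text.** It covers diagnosis, slide reading and randomisation. The margin is not mentioned again, and nothing relevant is marked as removed.

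**The concern.** A non-inferiority design needs four things before the data are read: an effect measure, an interval or test, its level, and a rule that sets the result against the margin. Only the margin is given. A cure percentage in each arm, even a correct one, does not say whether non-inferiority was shown.

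The nearest thing to an analysis method is Fisher's exact test in the list of sample-size inputs. Run in its ordinary form it asks whether the two rates are equal. A non-significant result there is not evidence of non-inferiority, and a significant one is not needed for it. The unstated sidedness of alpha is a second open choice. One-sided 0.025 corresponds to a 95% interval and one-sided 0.05 to a 90% interval, and these can give opposite answers on the same data.

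**Working it through.** **Inputs from the sample-size paragraph.** pT = 0.90, pC = 0.75, margin 0.068 below zero, power 0.80, 50 evaluable per group. Enrolling 60 and losing 20% leaves 60 × 0.8 = 48. Assumption: the planning rates apply to cure as the efficacy paragraph defines it.

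**1. The plan's own figure.** The distance from the planned difference to the margin is 0.15 + 0.068 = 0.218. For a non-inferiority score test (Farrington-Manning), the rates fitted under the null are 0.776 and 0.844.

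- Null variance: 0.776 × 0.224 + 0.844 × 0.156 = 0.3055.
- Alternative variance: 0.90 × 0.10 + 0.75 × 0.25 = 0.2775.
- n = (zα√0.3055 + 0.8416√0.2775)² / 0.218².
- One-sided 0.025: (1.0834 + 0.4433)² / 0.047524 = 49.05, so 50 per group.
- One-sided 0.05: 38.5, so 39 per group.

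Other formulas give other answers. The continuity correction is n′ = (n/4)(1 + √(1 + 4/(0.218n)))².

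| Method | one-sided 0.05 | one-sided 0.025 |
|---|---|---|
| Unpooled | 36.1 | 45.8 |
| Pooled | 37.6 | 47.7 |
| Score | 38.5 | 49.05 |
| Unpooled, continuity-corrected | 44.8 | 54.6 |
| Score, continuity-corrected | 47.2 | 57.9 |

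An ordinary two-sided superiority comparison at these rates needs 100 per group. The figure of 50 is therefore a non-inferiority size. It fits the score test at 0.025, but it also lies between the corrected values at the two levels.

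**2. One data set, two verdicts.** The Newcombe lower limit is d − √[(pT − lT)² + (uC − pC)²], where lT and uC are Wilson limits for each arm. Take 42/50 cured on adjunctive probiotic and 38/50 on metronidazole alone, so d = 0.08.

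- 95%: lT = 0.7149, uC = 0.8570. 0.08 − √(0.1251² + 0.0970²) = -0.078, below -0.068: not met.
- 90%: lT = 0.7377, uC = 0.8443. 0.08 − √(0.1023² + 0.0843²) = -0.053: met.

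Against the same 38/50, the 95% rule is first met at 43/50 (lower limit -0.056), where two-sided Fisher p = 0.308. Fisher p is 0.054 at 46/50 and first falls below 0.05 at 47/50 (0.023).

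**3. How often it matters.** These are exact sums over all pairs of binomial counts.

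| True rates 0.90 / 0.75 | n = 50 | n = 48 |
|---|---|---|
| 95% Newcombe limit above -0.068 | 0.832 | 0.806 |
| 90% Newcombe limit above -0.068 | 0.900 | 0.894 |
| Fisher p ≤ 0.05 (equal rates) | 0.410 | 0.386 |
| Margin met at 95%, Fisher p > 0.05 | 0.423 | 0.420 |

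The 95% and 90% rules disagree in 0.0675 of trials with 50 per group, and in 0.080 if both true rates are 0.75. With 48 per group at the planned rates they disagree in 0.894 − 0.806 = 0.088.

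At a true deficit equal to the margin (0.75 − 0.068 = 0.682 against 0.75), false non-inferiority with 50 per group is 0.026 at 95% and 0.053 at 90%. With 48 per group it is 0.027 and 0.051.

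**The case against.** The strongest reply is that the largest numbers rest on a use of Fisher's test that the plan never states. That is right. A reader might infer that the trial will be analysed by Fisher's test and so keeps only half its power (0.410 against 0.832). The documents do not support this: the test appears only among the sample-size inputs. The two powers also belong to different hypotheses, so their gap is not a loss that the plan causes. What stands is conditional. The only test named does not answer the sized question, and if it were used as an equality test, the two answers would often diverge.

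A reader might also infer that 50 per group shows the trial was sized at one-sided 0.025. It does not. The score test fits that level, but the plan names Fisher's test, and continuity-corrected sizes run from 44.8 to 47.2 at 0.05 and from 54.6 to 57.9 at 0.025. The level was simply not stated.

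A third tempting step is to make an analysis adjusted for baseline Nugent score the deciding one. Nothing in the plan calls for it, and any gain depends on a baseline effect that the documents do not give. It would also add a second open choice. In a simulation of 3000 trials with 50 per group, adjusted and unadjusted verdicts differed in about 1.5%, 5% and 8% for assumed odds ratios of 1, 2 and 3 per baseline point.

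Finally, recruitment ran from March to June 2019 and the document is dated February 2021. A rule added now may be only a reporting standard. That limits its value but does not remove the gap.

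**Conclusion.** The concern holds. The plan sizes a non-inferiority comparison and then gives no estimate, interval, level or rule with which to make it. The ambiguity that belongs to the plan itself is the interval level. It changes the verdict in 6.75% of trials at the planned rates (8.0% if both rates are 0.75) and moves false non-inferiority at the margin between 0.026 and 0.053. The 42% conflict with Fisher's test is larger, but it applies only if that test were run as a test of equal rates.

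The figures assume 50 evaluable women per group, independent binomial outcomes, Newcombe intervals, and planning rates that apply to the cure outcome as defined. That definition is not settled. The day-30 exclusion sentence leaves it unclear whether women scoring 7 or more at that visit stay in the cure denominator. A reader might take the cure definition alone to mean they count as not cured, but the next sentence prevents that reading from being taken as given. The Nugent cut at 7 is the trial's own criterion and is not in question.

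**What to change.** 1. State that the efficacy comparison is the risk difference in cure, adjunctive probiotic minus metronidazole, with an unadjusted Newcombe two-sided 95% confidence interval. Conclude non-inferiority only if the lower limit exceeds -0.068.
2. Present the 95% level (one-sided 0.025) as the conservative choice, with power of about 0.83 at 50 per group and 0.81 at 48. Say that 50 per group is consistent with it under a score test, without claiming that it was the level used.
3. If an analysis adjusted for baseline Nugent score is reported, label it a secondary sensitivity result that does not decide non-inferiority.
4. Reconcile the cure definition with the day-30 exclusion sentence, so that it is clear who is in the cure denominator.
5. Label the rule post hoc if outcomes by arm had been seen before it was written.

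The cost is a few lines of text and slightly more analysis on data already collected, with no new patients, visits or smears. The price is a stricter level than one-sided 0.05: power at the planned rates with 50 per group is 0.832 rather than 0.900.

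### Women BV-positive at day 30 are excluded and restored only for overall recurrence, so day-90 cure can become a responder-only rate and a day-30 cure effect can appear as a recurrence effect.

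*Combined protocol and SAP*

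**What the plan says.** All of this is in the combined protocol and SAP, under Study Protocol with SAP.

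- **Visits.** "Clinical follow-up visits were scheduled at 30 and 90 days after starting treatment". Metronidazole is given for 7 days and no smear is scheduled before day 30.
- **Outcome and analysis set.** "The efficacy outcome was evaluated by the cure rate according to per-protocol (PP) analysis". Cure is defined as the share of participants free of BV (Nugent score below 7) "at any of the follow-up visits".
- **Rule for day-30 positives.** The next sentence says that women with a Nugent score of 7 or more at day 30 were "excluded from the trial, but when we evaluate the overall recurrence rate of the 90-day follow-up, these participants were still included in".
- **Per-protocol set.** It is not defined. The nearest material is that "the compliance of participants was assessed by counting returned containers and filling out a questionnaire", which does not say who leaves the set.
- **Design rates.** "The sample size was calculated based on the non-inferiority test", with 0.90 in the test arm, 0.75 in the control arm and a margin of -0.068. No visit is attached to the two rates.

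**The concern.** The rule takes day-30 positives out of the trial and puts them back for one purpose, the 90-day recurrence rate. The cure rate gets no such exception. An analyst who follows the sentence as written would compute day-90 cure only among women negative at day 30. That group is selected by response to treatment, so the arms are no longer compared as randomised. Any benefit gained by day 30 also drops out of the day-90 comparison.

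The second problem holds on any reading of the cure rate. Every woman enters with a Nugent score of 7 or higher, and day 30 is the first follow-up visit. A woman positive then has not been shown to be free of BV, yet she is counted as a recurrence. If one arm clears more women by day 30, its overall recurrence is lower even when relapse after day 30 is the same in both arms.

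Cure is the only efficacy outcome that the plan defines, and neither researchers nor patients were blinded. The denominator should therefore not be open to choice.

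**Working it through.** **The plan's own figure.** The plan reports that "the sample size of each group was calculated as 50 patients, 100 patients in total". This reproduces with the Farrington-Manning non-inferiority formula at one-sided 0.025 and power 0.80:

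- distance to the margin: 0.90 - 0.75 + 0.068 = 0.218
- variance under the null, with restricted rates 0.776 and 0.844: 0.3055
- variance under the alternative: 0.90×0.10 + 0.75×0.25 = 0.2775
- n = (1.96×√0.3055 + 0.8416×√0.2775)² / 0.218² = 49.05, so 50 per group

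The sample size is not in dispute here. It supplies the 50 per group used below.

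**Assumptions.** (a) 90% and 75% are day-30 cure rates. (b) A share q of day-30-negative women stays negative at day 90, with q equal in both arms unless stated. The documents give neither.

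**Day-30 positives at 50 per group.** 50×0.10 = 5 in the test arm and 50×0.25 = 12.5 in the control arm.

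**Day-90 cure under the two denominators.**

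- Kept as failures (sustained cure): difference = 0.90q - 0.75q = 0.15q
- Dropped (responder-only): difference = q - q = 0

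| Equal relapse (1 - q) | Kept as failures | Difference | Dropped | Difference |
|---|---|---|---|---|
| 10% | 81% vs 67.5% | 13.5 points | 90% vs 90% | 0 |
| 20% | 72% vs 60% | 12 points | 80% vs 80% | 0 |
| 30% | 63% vs 52.5% | 10.5 points | 70% vs 70% | 0 |
| 40% | 54% vs 45% | 9 points | 60% vs 60% | 0 |
| 50% | 45% vs 37.5% | 7.5 points | 50% vs 50% | 0 |

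The gap exceeds 6.8 points whenever q > 0.068/0.15 = 0.453, that is, for equal relapse below about 55%. The margin is only a yardstick, because the plan does not apply it to a day-90 rate.

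**Unequal retention.** If 90% vs 80% stay negative, sustained cure differs by 0.90×0.90 - 0.75×0.80 = 0.81 - 0.60 = +21 points. The responder-only difference is +10 points: the same sign, about half the size.

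**Precision (Wald, two-sided 95% lower bound, 50 per group).**

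- Sustained, 20% relapse: 0.12 - 1.96×√(0.72×0.28/50 + 0.60×0.40/50) = -0.064
- Responder-only, 20% relapse, denominators 45 and 37.5: 0 - 1.96×√(0.80×0.20/45 + 0.80×0.20/37.5) = -0.173
- 10% relapse, same formulas: -0.034 and -0.130
- 30% relapse, same formulas: -0.088 and -0.199

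Against -0.068, the two denominators disagree at 10% and 20% relapse. At 30% both bounds lie outside.

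**What overall recurrence contains at 20% relapse.**

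| | Test | Control |
|---|---|---|
| Positive at day 30 | 10% | 25% |
| Negative at day 30, positive at day 90 | 0.90×0.20 = 18% | 0.75×0.20 = 15% |
| Overall recurrence | 28% | 40% |
| Day-30 positives as a share of events | 10/28 = 36% | 25/40 = 63% |

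The 12-point difference in overall recurrence arises although relapse among day-30-negative women is 20% in each arm.

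**The case against.** The strongest reply is that the plan defines one cure rate over both visits. A woman positive at day 30 has BV at a follow-up visit, so she fails it. On this view exclusion means only that follow-up stopped, and the re-inclusion clause carries her forward as a failure. Overall recurrence is then the complement of sustained cure, and the text is consistent. If exclusion applied to the day-30 rate too, cure at that visit would be 100% in both arms by construction, which cannot be intended.

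This reading is tenable, and it limits the point. It does not remove it. The phrase "at any of the follow-up visits" can also mean each visit taken in turn. Day-30 cure can then be computed before exclusion and day-90 cure after it, with no absurd result. The re-inclusion names only recurrence, and no definition of the per-protocol set decides the matter.

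It can also be said that the composite is disclosed: the rate is called overall, and the same sentence says who is counted. A careful reader can indeed see this. The name still invites reading a difference as one in relapse.

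A reader might infer that the rate counts women who never cleared BV. The documents do not support that. With no smear between the 7-day course and day 30, a day-30 positive may reflect persistence or early relapse. Only positive at day 30, and negative at day 30 but positive at day 90, can be told apart.

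Finally, the size is built on assumed inputs, and the zero follows from assuming equal relapse. That criticism stands; the figures show that the denominator can matter, not what happened in this trial.

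**Conclusion.** The point holds in a limited form and should be fixed. Taken literally, the exclusion rule restricts day-90 cure to day-30 responders; the cure definition also allows the opposite reading, and the plan does not choose. Independently, overall recurrence mixes two kinds of event, so a day-30 cure effect can show up as a recurrence effect.

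Under the stated assumptions, the choice of denominator moves the day-90 difference by 13.5 to 7.5 points for equal relapse of 10% to 50%. At 20% relapse it is 12 points vs 0. These sizes rest on treating 90% and 75% as day-30 rates and on assumed relapse. The gap in the text does not depend on them.

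Two stronger conclusions should not be drawn. One is that a responder-only rate was actually used, since the documents do not show which denominator was applied. The other is that the trial's non-inferiority conclusion would reverse: the margin is not tied to day 90, and the disagreement between the bounds is gone at 30% relapse.

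**What to change.** 1. Define day-90 efficacy as sustained cure: Nugent score below 7 at both day 30 and day 90. Keep day-30 positives in the denominator as failures, and state that a day-30 positive is not a reason to leave the per-protocol set.
2. Relabel overall recurrence as BV-positive at day 30 or day 90. Tabulate by arm its two observable components: positive at day 30; negative at day 30 and positive at day 90.
3. Present any rate among day-30-negative women as descriptive and non-randomised.
4. The document is dated 2021-02-20 and recruitment ran from March to June 2019, so a denominator chosen now may be informed by the data. State which denominator was used, and show both results if it was responder-only.

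The cost is wording, one extra table and a lower stated day-90 cure rate than a responder-only rate would give. No new smears are needed, because a day-30 positive has already failed sustained cure. The change concerns the analysis only. It removes this one source of selection and does not make a per-protocol comparison fully randomised.

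### The 90-day overall recurrence rate keeps day-30 failures but has no rule for day-30 negatives without a day-90 smear; either simple rule biases it modestly, and a two-stage estimate would not

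*Combined protocol and SAP*

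**What the plan says.** All the relevant text is in the combined protocol and SAP, under Study Protocol with SAP.

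- Visits: "Clinical follow-up visits were scheduled at 30 and 90 days after starting treatment".
- Day-30 failures: a woman with a Nugent score of 7 or more "in the 30-day follow-up was excluded from the trial". For the 90-day rate the efficacy paragraph then adds, "but when we evaluate the overall recurrence rate of the 90-day follow-up, these participants were still included in".
- Analysis set: "The efficacy outcome was evaluated by the cure rate according to per-protocol (PP) analysis". No other analysis set is named, and none is named for recurrence.
- Expected loss, in the sample size paragraph: "Considering a loss to follow-up rate of 20%, a sample size of 120 patients was finally determined, with 60 patients in each group". Neither its timing nor its split by arm is given.
- Blinding: "The study was not blinded to the researchers or the patients".

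The plan gives no numerator or denominator for the overall recurrence rate. It has no rule for a woman who is negative at day 30 and absent at day 90.

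**The concern.** The two groups that make up the 90-day rate are exposed to loss differently. A woman positive at day 30 has no further planned visit. The natural reading is that she enters the rate as a failure, and nothing later can take her out. A woman negative at day 30 has a day-90 status only if she attends. All loss after day 30 therefore falls on women who were still free of BV, and a crude proportion depends on how those women are treated.

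At stake is the accuracy of each arm's 90-day rate and, under some conditions, the difference between arms. The trial is open and only one arm takes an additional product for 30 days, so loss could differ by arm. The documents do not say that it will, or in which direction.

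**Working it through.** **The plan's own figures.** The plan states no recurrence rate to reproduce. Its loss allowance is 50 × 1.2 = 60 per arm. The 50 per arm is reproduced by a non-inferiority calculation at one-sided 0.025 with restricted (Farrington-Manning) variance and distance 0.90 − 0.75 + 0.068 = 0.218, which gives 49.05, so 50.

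**Inputs.** n = 60 per arm is from the plan. The rest are assumptions:
- p, failure at day 30
- r, relapse by day 90 among day-30 negatives; the documents give no value
- L, loss of day-30 negatives after day 30. The plan's 20% is used for size only, because the plan does not place it after day 30.

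Loss is first taken as unrelated to relapse.

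**Formulas.**
- Target (BV at day 30 or day 90): p + (1 − p)r
- Rule A, lost negatives dropped: [p + (1 − p)(1 − L)r] / [p + (1 − p)(1 − L)]
- Rule B, lost negatives counted as not recurrent: p + (1 − p)(1 − L)r

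**Example 1: p = 0.25, r = 0.20, L = 0.20.** There are 15 failures and 45 negatives; 36 negatives attend, 7.2 of them relapse, and 9 are lost.
- Target: 0.25 + 0.75 × 0.20 = 40.0%
- Rule A: (15 + 7.2)/(15 + 36) = 22.2/51 = 43.5%
- Rule B: 22.2/60 = 37.0%
- All lost negatives counted as recurrent: (22.2 + 9)/60 = 52.0%
- Two-stage estimate: 15/60 + (45/60) × (7.2/36) = 40.0%
- Greenwood variance of the two-stage estimate: 0.60² × [0.25/(60 × 0.75) + 0.20/(36 × 0.80)] = 0.36 × 0.0125 = 0.0045, so the standard error is 6.7 points. The 3.5-point bias under rule A is about half of that.

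**Range under rule A.** With L = 20%, p from 0.10 to 0.40 and r from 0.10 to 0.50, the excess is 1.1 to 4.9 points. With L = 10% it is 0.5 to 2.3 points.

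**Timing of loss.** Keep p = 0.25 and r = 0.20, but let 6 of 60 be lost before day 30 and 6 negatives after it. Of the 54 seen at day 30, 13.5 are positive and 40.5 negative; 34.5 negatives attend and 6.9 relapse. Rule A gives 20.4/48 = 42.5%.

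**Example 2: the planning cure rates read as cure over both visits.** Overall failure is 25% (metronidazole) and 10% (probiotic). Assume half of it occurs by day 30, and L = 20%.

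| Arm | Target | Rule A | Rule B |
|---|---|---|---|
| Metronidazole | 25% | (0.125 + 0.8 × 0.125)/(0.125 + 0.8 × 0.875) = 0.225/0.825 = 27.3% | 22.5% |
| Probiotic | 10% | (0.05 + 0.8 × 0.05)/(0.05 + 0.8 × 0.95) = 0.09/0.81 = 11.1% | 9.0% |
| Difference | 15.0 points | 16.2 points | 13.5 points |

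**Example 3: no treatment effect.** Take p = 0.20 and r = 0.20 in both arms, so the target is 36% in each. Assume losses of 30% (metronidazole) and 10% (probiotic).
- Rule A: (12 + 6.72)/(12 + 33.6) = 41.1% against (12 + 8.64)/(12 + 43.2) = 37.4%, a false 3.7 points favouring the probiotic.
- Rule B: 18.72/60 = 31.2% against 20.64/60 = 34.4%, a false 3.2 points the other way.

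**Other between-arm cases.** Equal p, r and L give a difference of exactly zero. Now take an equal overall rate of 40% and equal 20% loss, but day-30 failure of 10% in one arm (r = 1/3) and 25% in the other (r = 0.20). Rule A gives 0.34/0.82 = 41.5% against 0.37/0.85 = 43.5%, a false 2.1 points before rounding.

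**The case against.** The strongest reply is that no sentence says day-30 negatives count only if they return. Per-protocol is attached to the cure rate, so carrying it over to recurrence is an inference. This stands, and with it the direction of the bias is open: rule A pushes the rate up and rule B pushes it down. A reader might infer that the plan's rate is necessarily inflated. The documents do not support that.

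The 20% is an overall figure with no timing. This also stands. Only loss after day 30 produces this bias, so applying the full 20% there is an assumption.

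A reader might also take 25% and 10% as the plan's day-30 failure rates, add 20% relapse, and say that a true 12.0-point difference becomes 13.8. The plan does not tie its 75% and 90% to day 30, and it defines cure by freedom from BV across the follow-up visits. Under that definition, overall rates of 40% and 28% would mean cure of 60% and 72%, which contradicts the planning rates. Example 2 fits the plan better, and its distortion is about 1.2 points.

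Finally, the plan names cure as the efficacy outcome and specifies no between-arm test of recurrence. That limits the consequence. It does not make the rate well defined.

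**Conclusion.** The point holds as a cheap improvement. The plan fixes the treatment of day-30 failures and leaves the treatment of lost day-30 negatives open. If loss is unrelated to relapse, both simple ways of filling the gap give a biased rate: upward if these women are dropped, downward if they are counted as not recurrent. In the 25% example this is 43.5% or 37.0% against 40.0%. With the planning rates read as cure over both visits and half of failures by day 30, dropping gives 27.3% and 11.1% against 25% and 10%.

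A reader might infer that the rule by itself creates a difference between arms. It does not. With equal true rates, a false difference appears only if later loss, or the share failing by day 30, differs by arm. The 41.1% against 37.4% case rests on an assumed 30% and 10% loss that has no source in the documents.

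The relapse rate, the timing and split of loss, and the share failing by day 30 are all assumptions. The documents fix only that day-30 failures stay in, that some loss is expected, and that no rule covers the lost negatives.

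**What to change.** Define the overall 90-day rate as BV at day 30 or day 90 and estimate it by arm in two stages:

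P(BV at day 30) + P(no BV at day 30) × P(BV at day 90 | no BV at day 30, attended)

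Give it a Greenwood-type or bootstrap interval. State the numerator and denominator at each stage, use the same rule in both arms, and report by arm the number lost after day 30.

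The estimate assumes that loss among day-30 negatives is unrelated to relapse, which cannot be checked in an open trial with missing smears. Add bounds that count all lost negatives as recurrent and all as not recurrent (37.0% to 52.0% in the 25% example).

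The cost is a few lines of analysis wording and no new data. The interval is slightly less simple than a binomial one, and the difference between arms may look slightly smaller than the crude ratio would show.
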